5.3. Lifestyle Considerations

Participants will not be required to restrict or limit any of their normal lifestyle activities (eg, food and drink consumption; caffeine, tobacco, or alcohol consumption; exercise or physical activity) during this study.

5.4. Screen Failures

A screen failure occurs when a participant who has signed the ICF is not assigned to IMP. A minimal set of screen failure information (demography, screen failure details, eligibility criteria, SAE reports) is required to ensure transparent reporting of screen failure participants and address regulatory authority queries.

- Retesting: Participants with exclusionary clinical laboratory results, ECGs, vital sign measurements, etc that are inconsistent with their medical history or clinical evaluation, can be retested once within the remaining screening period to confirm the test value(s).
- Rescreening: Participants who do not initially meet this study's eligibility criteria can be rescreened once. For example, a participant who does not meet eligibility criteria because of an acute illness ongoing during screening (considering the illness itself does not violate inclusion/exclusion criteria), they can be rescreened once the illness is resolved or the medical issue stabilized. Rescreened participants will be reconsented and assigned a new participant number for the rescreening event.

5.5. Criteria for Temporarily Delaying Study Participation

As described in exclusion criterion 3B, participants with BP who have been treated with any of the following will be excluded from study participation:

- Sulfasalazine, IVIg, SCIg, immunoadsorption, or plasma exchange within 8 weeks of the baseline visit
- Tetracyclines (with nicotinamide [at doses higher than the RDA/DRI] or without nicotinamide) within 2 weeks of the baseline visit

• Any monoclonal antibody (including rituximab or another anti-CD20 biologic) within 6 months of the baseline visit

However, any potential ARGX-113-2009 candidate who has been treated with any of the above-noted therapies and still wishes to participate in the study must complete a wash-out period before they can be randomized to IMP. The duration of the required wash-out period must match the duration identified above for each class of medication. Note: therapy with TCS and/or conventional immunosuppressants (eg, azathioprine, cyclophosphamide, methotrexate, mycophenolate mofetil) or with dapsone requires no wash-out period; however, these therapies must be discontinued before baseline.

6. IMP(S) AND CONCOMITANT THERAPY

All IMP is manufactured according to Good Manufacturing Practice regulations.

6.1. IMP(s) Administered

A list of IMPs and noninvestigational medicinal products is presented in Table 5, while the characteristics of the 2 treatment arms of ARGX-113-2009 are described in Table 6. Fixed doses of efgartigimod PH20 SC or placebo will be administered at body sites spared of any cutaneous BP lesions, with the abdominal area being the preferred site. Optional sites (such as thighs and arms) may be used. Placebo will contain the same excipients as efgartigimod PH20 SC but without the active ingredient efgartigimod. Masked vials and masked syringes will be provided to preserve the study blind (Section 6.2.1 and Section 6.3).

Refer to the pharmacy manual and preparation guide for further details.

Table 5: IMP(s) Administered

IMP label	Efgartigimod PH20 SC	Placebo	Oral prednisone ^a				
IMP and non-IMP name	Efgartigimod for SC administration coformulated with rHuPH20	Placebo	Prednisone for oral administration				
IMP description	Solution for SC injection to be administered at a fixed efgartigimod dose of 1000 mg per injection	Vehicle + 2000 U/mL rHuPH20 for SC injection	Prednisone (or equivalent) tablets for oral administration				
Type	Biologic	Other: placebo	Non-IMP				
Dose formulation	Injection	Injection	Tablet				
Unit dose strength(s)	Efgartigimod 180 mg/mL + 2000 U/mL rHuPH20	Placebo + 2000 U/mL rHuPH20	Prednisone (or equivalent) 2.5 mg, 5 mg, 10 mg, 20 mg				
Dosage level(s)	× 1000 mg SC doses administered at separate sites (ie, mg in total) on day 1 and day 8; single 1000 mg SC doses administered weekly from week 2 through week 35	SC doses administered at separate sites on day 1 and day 8; single SC doses administered weekly from week 2 through week 35	Refer to Section 6.8.1.3 for oral prednisone dosage taper/increase schedule				
Route of administration	Abdominal SC injection(s); preferred site ^b	Abdominal SC injection(s); preferred site ^b	Oral administration				

Table 5: IMP(s) Administered (Continued)

Intervention	Efgartigimod PH20 SC	Placebo	Oral prednisone ^a				
Use	Investigational drug	Placebo control for investigational drug	Non-IMP; concurrent therapy				
IMP and non-IMP	IMP	IMP	Non-IMP				
Sourcing	Provided by the sponsor to the study site	Provided by the sponsor to the study site	Provided by the sponsor to the study site. Local sourcing is permitted only if no doses are available at the site and only after consultation with the sponsor (or designee)				
Packaging and labeling	Provided in glass vials. Each glass vial will be labeled as required per country requirement	Provided in glass vials. Each glass vial will be labeled as required per country requirement	Non-IMP will be provided as 1 of the following: In the commercial package and labeled as required per country requirements As a magistral preparation upon prescription by the investigator In the commercial package sourced locally				

BP=bullous pemphigoid; efgartigimod PH20 SC=efgartigimod for SC administration coformulated with rHuPH20; IMP=investigational medicinal product; OCS=oral corticosteroid (prednisone or equivalent); placebo=placebo for SC administration coformulated with rHuPH20; rHuPH20=recombinant human hyaluronidase PH20; SC=subcutaneous(ly)

^a Refers to oral prednisone or an equivalent OCS.

^b IMP will be administered on body sites spared of any cutaneous BP lesions; the abdomen is the preferred site. Optional sites (such as thighs or arms) may be chosen.

Table 6: Study Arm(s)

Arm Title	Efgartigimod PH20 SC	Placebo			
Arm Type	Experimental	Placebo			
Arm Description	Participants will receive efgartigimod PH20 SC mm mg (via separate 1000 mg SC injections) on day 1 and day 8	Participants will receive placebo (via separate SC injections) on day 1 and day 8			
	Beginning at week 2, participants will receive efgartigimod PH20 SC 1000 mg (via single SC injection) once weekly through week 35.	Beginning at week 2, participants will receive placebo (via single SC injection) once weekly through week 35.			
	Participants will be administered concurrent OCS (oral prednisone) at 0.5 mg/kg/day, or equivalent OCS) beginning at baseline (week 0); this dosage will be adjusted throughout the study based on the participant's current BP disease status.	Participants will be administered concurrent OCS (oral prednisone) at 0.5 mg/kg/day (or equivalent OCS) beginning at baseline (week 0); this dosage will be adjusted throughout the study based on the participant's current BP disease status.			
Associated Labels	Efgartigimod PH20 SC OCS	Placebo OCS			

BP=bullous pemphigoid; efgartigimod PH20 SC=efgartigimod for SC administration coformulated with rHuPH20; IMP=investigational medicinal product; OCS=oral corticosteroid (prednisone or equivalent); placebo=placebo for SC administration coformulated with rHuPH20; rHuPH20=recombinant human hyaluronidase PH20; SC=subcutaneous(ly)

6.2. Preparation, Handling, Storage, and Accountability

Details about the use of concurrent oral prednisone (or equivalent OCS) are described in Section 6.8.1.

6.2.1. Preparation

Efgartigimod PH20 SC will be provided as a sterile, clear to opalescent, colorless to yellowish solution for SC injection in masked glass vials.

Placebo will be provided as a sterile, colorless, clear solution for injection in masked glass vials. These vials will contain the same formulation as the efgartigimod PH20 SC solution for injection, but without the active ingredient (efgartigimod).

Trained and authorized study staff will use an amber colored syringe for preparation and administration of IMP: refer to Section 6.3 for details.

The IMP will be manufactured in accordance with Good Manufacturing Practice (GMP) regulations.

Detailed instructions for IMP management at the study site are included in the pharmacy manual. Instructions on the preparation and administration of IMP (including the volume of IMP to be administered) will be included in the on-site guide and the home administration guide.

6.2.2. Handling

The investigator or designee must confirm that appropriate temperature conditions have been maintained during transit for all IMP that has been received. Any discrepancies are reported and resolved before the use of any IMP.

Participants who will be administered IMP during home visits (Table 1) will be given IMP to take home with them at their preceding on-site visit. Participants will be responsible for the correct handling of IMP and will return any used and unused portion back to the study site at their next on-site visit. In the event that COVID-19 pandemic travel/lockdown restrictions are in effect or on-site visits pose a potential risk to participants or site staff, IMP will be shipped to participants per courier.

Only ARGX-113-2009 participants may receive IMP. Participants and/or their caregivers will be invited to receive training for (self-)administration of the IMP. In this study, participants (and/or their caregivers) will only be permitted to (self-)administer IMP at on-site visits under the supervision of site staff, and only after they have completed training and are determined competent enough to do so by site staff. During home visits, IMP may only be administered by a trained and authorized home nurse.

6.2.3. Storage

Both efgartigimod PH20 SC and placebo will be supplied to the pharmacy or dedicated site location at the study site by and under the responsibility of the sponsor's designated IMP supply vendor. For each IMP batch at the site, the investigator will receive the certificate of analysis, certificate of conformity, and European Union qualified person release documents.

All IMP must be stored in a secure, environmentally controlled, and monitored (via manual or automated system) area in accordance with the labeled storage conditions with access limited to the investigator and authorized site staff. Detailed instructions are included in the pharmacy manual.

The IMP must be stored refrigerated (2°C to 8°C [36°F to 46°F]) in its secondary packaging, should not be exposed to freezing temperatures, should not be shaken, and should be protected from direct sunlight during storage at the investigative site.

The investigator (or designee) is responsible for the correct and safe storage of the IMP assigned to the investigative site, in a locked, secure storage facility with access limited to those individuals authorized to dispense the IMP and maintained within the appropriate temperature ranges.

For home administration, the participant is responsible for the correct storage of IMP.

Detailed instructions on accountability for the IMP will be included in the pharmacy manual.

6.2.4. Accountability

The investigator, institution, or the head of the medical institution (where applicable) is responsible for IMP accountability, reconciliation, and record maintenance (ie, receipt, reconciliation, and final disposition records).

All used and unused IMP should be returned to the investigator at each dispensing visit. Additional guidance and information for the final disposition of used and unused IMP are provided in the pharmacy manual.

6.2.5. Packaging and Labeling

Packaging and labeling information is presented in Table 5. Additional information is included in the pharmacy manual.

6.3. Measures to Minimize Bias: Randomization and Blinding

The site will enroll the participant and a unique participant ID will be automatically allocated through interactive response technology (IRT) at the first screening visit.

The results of all screening procedures have to be available before baseline (week 0) to determine the eligibility for entering the study. Randomization should be performed as soon as the participants meet the appropriate criteria to begin treatment.

Upon confirmation of eligibility at baseline (week 0), the participant will be randomized through IRT. Participants will be randomized in a 1:1 ratio to receive efgartigimod PH20 SC or placebo.

At randomization, part B participants will be stratified by region (China, Japan, rest of the world). Participants who comprise the "rest of the world" stratum will be further stratified by disease history (newly diagnosed or relapsing) and disease severity (severe [IGA-BP score of 4] or moderate [IGA-BP score of 3]).

Because this is a randomized, double-blinded study, access to the IMP treatment assigned will be limited. No study team members from the investigating staff, sponsor staff who are directly involved in study management, or sponsor designees (except for staff at specialized laboratories who are responsible for PK, PD, and ADA analysis) will have access to the information related to IMP treatment assigned until after database lock.

Efgartigimod PH20 SC is a colorless to yellowish solution, while placebo is a colorless solution. To ensure that participants and site staff remain blinded to IMP, both efgartigimod PH20 SC and placebo will be provided in masked glass vials; additionally, amber-colored syringes will be used for the preparation and administration of IMP (Section 6.2.1).

An independent unblinded data and safety monitoring board (DSMB), including an independent statistician, will review all unblinded safety data as specified in Section 10.1.5.

6.3.1. Emergency Unblinding

This is a double-blinded study. The IRT will be programmed with blind-breaking instructions. In case of an emergency, the investigator is solely responsible for determining if unblinding of the IMP assignment is necessary. Participant safety must always be the first consideration in making such a determination. If the investigator decides that unblinding is warranted, the investigator

can contact the sponsor before unblinding a participant's IMP unless this could delay emergency treatment for the participant. If a participant's IMP assignment has been unblinded, the sponsor must be notified within 24 hours of this occurrence. The date and reason for the unblinding must be recorded in the source documents.

If the blind is broken by the investigator, then it may be broken only for the participant concerned, and the IMP treatment assignment should not be revealed to the study team members from the sponsor, nor from the sponsor's designee, pharmacy staff, or other site staff. Once unblinded, IMP will be permanently discontinued (Section 7.1.1).

6.4. Study Compliance

Participants will receive IMP under medical supervision at the site. The date and time of each dose administered will be recorded in the source documents.

Participant compliance with IMP administration at home will be assessed by direct questioning during the site visit and documented in the source documents and relevant forms. Deviation(s) from the prescribed dosage regimen will be recorded.

For each injection, the start and end times (hour and minute) and details of any interruptions or premature discontinuation of each injection will be recorded on the eCRF. The start time will be when the syringe plunger begins to be pressed; the end time will be when the administration of the total volume of IMP is finished. [Note: For the baseline (week 0) and week 1 IMP injections, site staff must record the start and end times (and the details of any interruptions or premature discontinuation of injections) for each of the injections of IMP administered to participants on those days.]

The sponsor's designee will review the pharmacy records at each investigative site, including the IMP accountability and dispensing records. The sponsor's designee will compare the dispensing record and vials with the individual participant's identifiers, kit number, and visit schedule to confirm that the participant received the correct treatment and dose, and that the dosing schedule is correct.

Errors that are identified will be discussed with site staff to ensure they are not repeated. The sponsor designee's report will include details of any missed doses, errors in dose, treatment or scheduling errors, and the associated explanations. The sponsor will determine whether these dosing errors will be reported as protocol deviations in the clinical database. All supplies and pharmacy documentation must be made available throughout the study for the sponsor designee to review.

The investigator should promote treatment compliance by stating that compliance is necessary for the participant's safety and the validity of the study. The prescribed dose, timing, and mode of administration cannot be changed. Any deviations from the intended regimen must be recorded on the eCRF.

Training for (self-) administration of IMP

Participants and/or their caregivers will be invited to receive training for (self-)administration of the IMP. In this study, participants (and/or their caregivers) will only be permitted to (self-)administer IMP at on-site visits under the supervision of site staff, and only after they have completed training and are determined competent enough to do so by site staff. The IMP doses at

baseline (week 0) and week 1 must be administered by the investigator or designee under medical supervision. Starting at week 2, participants or caregivers can choose to be trained in IMP (self-)administration. Note that successful completion of this training is intended to enable self-administration or caregiver-supported administration at home in the OLE study ARGX-113-2010.

6.4.1. Handling Missed Doses of the IMP

All efforts will be made to ensure that the participant receives all administrations of IMP on the days scheduled (within the allowed visit windows).

Incidents of missed IMP doses will be recorded on the eCRF, along with the reason(s) why the dose was missed. These reasons will be assessed by the investigator, site staff, and sponsor, who will agree upon and implement an appropriate set of actions to minimize the possibility of subsequent missed IMP doses.

Participants who meet either of the following conditions will be excluded from the per-protocol analysis set:

- Participants who miss a cumulative total of >50% of their scheduled doses of IMP
- Participants who miss 3 or more consecutive scheduled doses of IMP

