4.1.2. Conduct of Both Parts A and B

Parts A and B of the study have different sample sizes; otherwise, both parts are identical in schedule, structure, assessments, and conduct. Both parts A and B have screening periods

of up to 2 weeks (extendable to 3 weeks per investigator discretion) followed by treatment periods of 36 weeks, during which participants will receive either efgartigimod PH20 SC or placebo. Finally, all part A and part B participants who complete the end of treatment period (EoTP) visit at week 36 will be offered the option to either enroll in an open-label extension (OLE) study or complete a 7-week treatment-free follow-up period.

To enter the study, participants must have a diagnosis of BP that complies with the international guidelines for the diagnosis of BP. ^{19,20,21} The diagnosis of BP must be confirmed by all 3 of the following methods before the participant is randomized to a study arm (refer to inclusion criterion 3):

- Clinical signs of BP (presence of bullae), with or without the presence of urticarial, eczematous, or erythematous plaques, and with or without pruritus.
- Histopathological and direct immunofluorescence (DIF) examination of a cutaneous biopsy.
- Serology by indirect immunofluorescence (IIF), chemiluminescence enzyme immunoassay (CLEIA), or ELISA.

In part B, study participants will be stratified by disease history (newly diagnosed or relapsing) and disease severity (moderate BP [an Investigator Global Assessment of Bullous Pemphigoid {IGA-BP} score of 3] or severe BP [an IGA-BP score of 4]). The participants will be randomized in a 1:1 ratio to receive either efgartigimod PH20 SC or placebo as follows:

- Efgartigimod PH20 SC will be administered by SC injection on day 1 and day 8 at a dose of mg (administered as separate SC injections of 1000 mg each), followed by single weekly SC injections of 1000 mg from week 2 through week 35.
- Placebo (injection vehicle coformulated with 2000 U/mL of rHuPH20) will be administered using the same regimen described above.

All participants will also receive concurrent therapy with OCS, ie, prednisone at a starting dosage of 0.5 mg/kg/day at baseline, or an alternate OCS at an equivalent dose strength. The OCS dosage will be adjusted according to each participant's BP disease status throughout the study. BP disease status terminology definitions are listed in Section 4.1.3 and the oral prednisone dose adjustment procedure is described in Section 6.8.1.3.

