6.8.1.3. Oral Prednisone Dose Adjustment Regimen (Based on BP Disease Assessment)

Participants will receive IMP with concurrent OCS therapy. The recommended OCS dosing regimen is described below and displayed in Table 7.

The investigator should not deviate from the concurrent oral prednisone dosing regimen, except in matters where the safety of the participant may be compromised. After taking appropriate action to ensure the safety of the participants, such concerns should be documented and communicated to the sponsor's medical monitor and designee within 24 hours of the event.

For OCS doses not listed in Table 7, minimum and maximum recommended doses are provided. For participants with body weights of <45 kg or ≥110 kg, the investigator should propose OCS doses and inform the medical monitor to ensure consistency within the study.

Note: For the following list, "oral prednisone" refers to prednisone or an alternate OCS of equivalent dose strength.

- All participants will begin the study by taking oral prednisone 0.5 mg/kg/day starting at baseline (week 0; day 1).
- If the participant has not achieved CDA within 1-3 weeks of treatment with oral prednisone 0.5 mg/kg/day, then the dosage may be increased to 0.75 mg/kg/day for up to an additional 3 weeks. This period may be extended by 1 additional week (based on clinical judgment) to achieve CDA with an oral prednisone dosage of either 0.75 mg/kg/day or 1 mg/kg/day.

- A participant will be considered as a treatment failure if they do not achieve CDA after receiving the IMP with the prednisone dosing regimen described above. In case of treatment failure, IMP will be permanently discontinued (Section 7.1.1). Under these circumstances, the participant will be considered a nonresponder (Section 9.3.2).
- When CDA is achieved, the oral prednisone dosing regimen is adjusted as follows:
 - After CDA has been sustained for ≥2 weeks, the dose tapering schedule begins with the next lower oral prednisone dosage as listed in Table 7. Each new dosage must be maintained for at least 2 weeks provided that no new lesions (transient or nontransient) appear. Duration of tapering steps from escalated doses (>0.5 mg/kg/day) may be shortened based on clinical judgment.

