2. GENERAL METHODOLOGY

2.1 ANALYSIS SETS

2.1.1 Analysis sets

The following analysis sets will be considered in the statistical analysis:

All screened participants who signed the informed consent form

participants set (SCR): (ICF) to participate in the study

Full analysis set (FAS): all participants who were randomized into the study

Safety analysis set all randomized participants who received at least one

(SAF): dose of IMP

Per Protocol set (PP): All FAS analysis set participants who did not have an

important protocol deviation impacting the efficacy results. The determination of the per-protocol population will be finalized and documented prior

to database lock and unblinding.

PK analysis set (PK) all participants in the safety analysis set for whom at

least one post-baseline serum PK concentration is

available, excluding placebo participants

PD analysis set (PD) all participants in the safety analysis set for whom at

least one post-baseline serum PD result is available

Note: Having signed an informed consent is defined as having a complete informed consent signature date in the database.

The efficacy analyses will be done on the FAS analysis set. Sensitivity analyses of primary and key secondary efficacy endpoints will be done on the PP analysis set. The general characteristics and safety analyses will be done on the safety analysis set. PK analysis will be performed on the PK analysis set. PD analysis will be done on the PD analysis set.

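### The protocol's missed-dose rule for the per-protocol set has no exception for required IMP stops and does not match Table 8 or SAP 2.1.1; on one open reading the sensitivity analyses would drop participants because of their outcome

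*Protocol*

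**What the plan says.** Protocol 6.4.1 states: "Participants who meet either of the following conditions will be excluded from the per-protocol analysis set". The two conditions are "Participants who miss a cumulative total of >50% of their scheduled doses of IMP" and "Participants who miss 3 or more consecutive scheduled doses of IMP". The section asks for the reason for each missed dose to be recorded, but the exclusion does not depend on that reason.

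Dosing is weekly. After the day 1 and day 8 visits, Protocol 4.1.2 gives "single weekly SC injections of 1000 mg from week 2 through week 35".

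Several outcomes end dosing by rule. Protocol 6.8.1.3 says "In case of treatment failure, IMP will be permanently discontinued" and calls such a participant a nonresponder. Protocol 6.8.3 and 7.1.1 also require a permanent stop after a second relapse or steroid toxicity. These participants are encouraged to stay in the study to week 36.

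The PP set is defined differently elsewhere. Protocol Table 8 takes FAS participants without a major protocol deviation affecting efficacy. SAP 2.1.1 says the same with an important deviation. Neither mentions missed doses, and SAP 6.1, which lists departures from the protocol, does not list dropping the 6.4.1 rule.

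On the role of the set, SAP 2.1.1 says: "Sensitivity analyses of primary and key secondary efficacy endpoints will be done on the PP analysis set".

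**The concern.** A PP analysis is meant to show whether the result holds among participants treated as planned. A participant who fails treatment and is then stopped as the protocol requires has been treated as planned. Removing that person selects on the outcome under study, and the share removed may differ by arm.

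Key secondary endpoint 3 (control of disease activity, then no relapse through week 36) shows this most clearly. Treatment failure is defined as absence of disease control, and a second relapse is a relapse. Participants stopped for either reason have already failed that endpoint, so excluding them excludes endpoint failures as such.

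The normalized cumulative OCS dose is also affected. It covers the on-IMP period, which treatment failures spend at the starting or an escalated prednisone dosage without tapering. Removing them removes high values.

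At stake is how to read agreement or disagreement between PP and FAS. For four of the five key secondary endpoints, SAP Table 4 lists no robustness analysis other than PP; only the OCS dose endpoint also has a treatment-policy analysis.

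**Working it through.** The plan gives no figure for PP membership, so there is none to reproduce.

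**Step 1: who meets the rule if doses after a permanent stop count as missed**

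- Dosing visits: weeks 0 to 35, which is 36.
- Doses missed after a permanent stop = 35 − week of last dose.
- Time to treatment failure (Protocol 6.8.1.3): the first stage, at the starting dosage, lasts 1 to 3 weeks. For the second stage the text is "the dosage may be increased to 0.75 mg/kg/day for up to an additional 3 weeks", and 1 optional extra week can follow. Earliest 1 + 3 = week 4; latest 3 + 4 = week 7.
- The last dose falls in the week of declaration or the week before, so between week 3 and week 7. Missed: 35 − 3 = 32 (32/36 = 89%) down to 35 − 7 = 28 (28/36 = 78%). Both conditions are met throughout.
- More than 50%: last dose at week 16 gives 19/36 = 52.8% (met); week 17 gives 18/36 = 50.0% (not met).
- Three in a row: last dose at week 32 misses weeks 33, 34 and 35 (met). Among permanent stops, only a last dose at week 33 or 34 escapes both conditions.

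**Step 2: how the FAS primary analysis scores the same people**

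| Group | Primary FAS analysis | Source |
|---|---|---|
| Treatment failure | Nonresponder | Protocol 6.8.1.3 |
| Stop for lack of efficacy | Nonresponder | Protocol 9.3.2, SAP 4.1.2.2 |
| Rescue therapy before week 36 | Nonresponder | SAP 4.1.2.2 |
| Stop for another reason, e.g. AE | Not a nonresponder by rule; still treated as receiving IMP | SAP 4.1 |

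A steroid-toxicity stop without rescue therapy belongs in the last row unless its reason is recorded as lack of efficacy.

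**Step 3: possible effect on the PP odds ratio**

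Assumptions: FAS response of 20% on placebo and 50% on efgartigimod, the scenario of the SAP 1.4.2.1 simulation (the protocol's own rates are blacked out); 60 per arm; all efficacy-driven stops are nonresponders and all are removed. The stop rates s are assumed, because the documents give none: 15-35% on placebo, 5-15% on efgartigimod.

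PP rate = FAS rate / (1 − s). PP odds are 0.5/(0.5 − s_E) on efgartigimod and 0.2/(0.8 − s_P) on placebo, so

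PP odds ratio = 2.5 × (0.8 − s_P)/(0.5 − s_E).

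With no stops this is 2.5 × 0.8/0.5 = 4.0, the FAS value.

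| s_P | s_E | PP rates, placebo vs efgartigimod | PP n | PP odds ratio |
|---|---|---|---|---|
| 15% | 5% | 23.5% vs 52.6% | 51 + 57 = 108 | 2.5 × 0.65/0.45 = 3.61 |
| 15% | 15% | 23.5% vs 58.8% | 51 + 51 = 102 | 2.5 × 0.65/0.35 = 4.64 |
| 35% | 5% | 30.8% vs 52.6% | 39 + 57 = 96 | 2.5 × 0.45/0.45 = 2.50 |
| 35% | 15% | 30.8% vs 58.8% | 39 + 51 = 90 | 2.5 × 0.45/0.35 = 3.21 |

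The rates rise in both arms. The odds ratio stays at 4.0 only if the same share of nonresponders is removed from each arm: s_P/0.8 = s_E/0.5, or s_P = 1.6 × s_E. Otherwise it moves down or up.

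**Step 4: no true effect**

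With 12/60 responders in each arm, the PP odds ratio is (1 − f_P)/(1 − f_E), where f is the share of nonresponders removed. Removing 50% on efgartigimod and 25% on placebo gives 0.75/0.50 = 1.5; the reverse gives 0.50/0.75 = 0.67.

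**The case against.** The strongest reply is that the rule was never meant to reach participants who have stopped. Section 6.4.1 treats a missed dose as an incident with a reason, followed by steps to prevent the next one, which fits people still on IMP. Permanent discontinuation has its own section. Table 8 and SAP 2.1.1 rest on deviations, and a stop the protocol requires is not obviously one. PP membership is to be finalized before lock and unblinding.

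This stands as far as it goes. A reader might infer that the rule certainly deletes all treatment failures; the documents do not say so. They do not say the opposite either. Table 1 schedules IMP weekly, visits continue on schedule after a stop, and the 6.4.1 exclusion is mandatory whether or not there is a deviation. A programmer could defensibly count those doses as missed.

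A reader might also infer that everyone removed is a nonresponder in the primary analysis. That is not supported: under SAP 4.1, AE and other non-efficacy stops are not nonresponders by rule, so the rule could also remove responders. Nor would all nonresponders go, since those who stay on IMP remain in the set.

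Finally, PP is a sensitivity set. The alpha-controlled tests use the FAS, and the primary endpoint also has an exact logistic regression and a treatment-policy analysis with multiple imputation on the FAS. That limits the damage but does not make the PP analyses interpretable.

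**Conclusion.** The point holds as a conflict between three passages and an undefined count. On the literal reading, every treatment failure is removed, as is any second-relapse or steroid-toxicity stop with a last dose at week 32 or earlier. The PP analyses of the primary and key secondary endpoints would then condition on outcome. On the deviation-based reading these participants might stay.

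The size cannot be fixed from the documents. Under the assumed rates, the PP odds ratio runs from about 2.5 to 4.6 against 4.0. It is tempting to conclude that PP must understate the effect and lose power; the documents do not support a direction, since that depends on unknown stop rates by arm. Nor is the primary result in doubt: the FAS analysis and the fixed-sequence testing are unaffected. The point is worth correcting because the remedy is cheap, not because the main conclusion is at risk.

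**What to change.** Before database lock and unblinding, make Protocol 6.4.1, Protocol Table 8 and SAP 2.1.1 give one PP definition.

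- Apply both missed-dose conditions only to doses scheduled up to permanent IMP discontinuation. Participants stopped for treatment failure, second relapse or other lack of efficacy then stay in the PP set and are scored under each endpoint's intercurrent-event and rescue rules.
- State separately how doses withheld for safety stops (Protocol 7.1.1) or temporary interruptions (7.1.2, 8.4.7.1) are counted. Three weekly doses withheld for an infection could otherwise exclude a compliant participant who is still on treatment. Whether to keep such participants is a legitimate choice about adequate exposure, but it should be made in advance.

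The cost is a sentence or two in the SAP and the PP specification. No new data are needed and no clinical rule changes. The downside is that the PP set will include some participants with short exposure.
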